8.12 Monthly CareLink Transmissions

Subjects are required to perform a manual device transmission monthly from the time they are enrolled in the study until their Study Exit visit. [REDACTED]

[REDACTED] The subject will utilize the MyCareLink® Home Monitor to manually transmit the data. The subject will receive instructions on how to perform the manual transmission. Refer to Appendix G.

As described above, a Monthly Device Transmission eCRF will be required to be completed to ensure the subject manually transmitted. A study deviation will be required for any missed monthly manual Carelink transmissions, unless a device interrogation file for an interrogation occurring within the required timeframe is provided to Medtronic.

8.13 Device Interrogation

For all follow-up visits occurring in the office, a full “interrogate all” final device interrogation file (.pdd) must be obtained and saved in a digital format (USB). The original file must be stored at the site and a copy sent to Medtronic. It is recommended that data are not cleared during any interrogation. This should be conducted at the end of the visit.

8.14 Healthcare Utilization

Cardiovascular-related Health Care Utilizations (HCUs) (including hypervolemia and hypovolemia) will be collected. This includes the following:

- Unscheduled clinic visit (including subject-initiated phone calls if the subject is experiencing CV-related symptoms)
- Scheduled clinic visit (if the subject is experiencing CV-related symptoms)
- Hospital outpatient clinic visit
- Urgent care visit
- Other outpatient utilization with overnight stay
- Emergency department visit
- Inpatient hospitalization

HCU information should be reported upon center awareness and assessed at all visits including the monthly telephone visits. If multiple HCUs occur within the same day, data from all HCUs can be captured on one eCRF.

8.15 System Modification

A system modification will be reported in the event the device requires invasive modification (e.g., device explant, device reposition). In the event of a system modification, the follow-up schedule for the subject will remain unchanged. For a system modification the following activities are required:

- Complete the System Modification eCRF
- Device interrogation (media/USB)
- Any Reveal LINQ™ system and procedure-related adverse events
- Any healthcare utilizations
- Any device deficiencies or study deviations

If the device is taken out of service (e.g., explanted) and a replacement will not be implanted or the replacement is not a study approved device, the subject must be exited from the study after all device and/or procedure related AEs have been resolved or remain unresolved with no further action planned.

All explanted product (device) should be returned to Medtronic for analysis when permissible by local laws and regulations. See Section 9 for final product disposition details.

In the event that a subject has a re-attempt after a previous unsuccessful system modification, the subsequent attempt(s) must be reported via eCRF as separate system modifications.

8.16 Study Exit

A Study Exit eCRF is required for all subjects except in the case of death. Prior to exiting a subject from the study, it is recommended to follow the subject until all ongoing device and/or procedure related AEs are resolved or unresolved with no further actions planned. Following exit, subjects will continue to receive standard medical care. Upon exiting from the study, no further study data will be collected or study visits will occur for the subject. All data available through the time of the subject's exit will be used for analysis.

Subjects are urged to remain in the study as long as possible but may be exited from the study for any of the following situations and will be documented on the Study Exit eCRF:

- Subject did not meet inclusion/exclusion criteria
- Subject was not inserted with a Reveal LINQ™ device
- Reveal LINQ™ removal without re-implantation
- Implant attempted, however no Reveal LINQ™ was implanted
- Subject relocation to another geographic location
- Subject chooses to withdrawal
- Investigator chooses to withdraw a subject
- Subject lost to Follow-Up
- End of battery life of LINQ™ device
- Study Termination

The following information/procedure is to be collected/performed at study exit:

- Reason for exit
- Removal of the LINQ™ HF investigational RAMware from the LINQ™ device
- Medications
- Device interrogation (media/USB)
- Any Reveal LINQ™ system and procedure-related adverse events
- Any healthcare utilizations
- Any device deficiencies or study deviations

In the case that the subject is determined to be lost to follow-up, details of a minimum of two attempts and the method of attempt (e.g., one letter and one phone record or two letters) to contact the subject must be recorded. In addition, follow the regulations set forth by the governing IRB.

If discontinuation is because of safety or lack of effectiveness, the subject shall be asked to be followed for collecting safety data outside the clinical investigation.

8.17 Medications

Cardiovascular medications will be collected at the baseline assessment, 1 Month, 6 Month, 12 Month office visits and Study Exit. The name, dose, frequency and route of all cardiovascular medications will be collected. Changes to medications will be captured at healthcare utilizations.

There are no medications that are required for this study although some medications may be administered in treating specific conditions at the discretion of the physician. The only medications that are excluded from use during this study are investigational.

8.18 6 Minute Hall Walk Test

Subjects will be asked to perform a 6 Minute Hall Walk test at the 1 Month, 6 Month and 12 Month office visits. A Holter will be recommended to be worn during the 6 Minute hall walk at the 6 Month Visit only. In addition, the subjects will be asked to press the Patient Assistant device to mark the beginning and end of their 6 Minute Hall Walk test ONLY when the DR220 Holter is not used. Refer to Appendix C for more details.

[REDACTED]

[REDACTED]

[REDACTED]

[REDACTED]

8.21 Review of Data Recorded by the Reveal LINQ™ Device

Reveal LINQ™ data derived from the LINQ™ HF investigational RAMware will not be viewable to the site. The standard arrhythmia data from the LINQ™ device will be viewable via Carelink.

8.22 Holter

Subjects may be asked to have a Holter placed to collect some additional information from the LINQ™ device. The DR220 Holter Recorder used in this study is a portable ECG device able to collect continuously telemetered signals from any Medtronic device for up to 48 hours. The Holter Recorder has application for any subject with a Medtronic ICM. For the purposes of this study, the intended use of the Holter Recorder is to acutely uplink continuous [REDACTED] signals that will be collected by the LINQ™ HF RAMware in the Holter mode. The intended use of Holter mode is for a short duration of less than 30 minutes during the 6 minute hall walk test during an office visit.

Since only the device data uplink feature of the Holter will be used in this study, the device antenna will only be used and no ECG electrodes will be used. Please refer to Appendix C for more details.

9 INVESTIGATIONAL DEVICE/RAMWARE STORAGE, HANDLING AND TRACEABILITY

The following section details tracking of all clinical investigation study components. Study components will be distributed to a center only when Medtronic has received all required documentation and has notified the center of center activation.

Distribution of study components to study centers during the clinical study will be managed by Medtronic. All product must be stored in a secure location at the site. It is the responsibility of the investigator to correctly handle, store, and track the study products maintained at the site. Study components will be used only in the study according to the CIP.

Product Distribution logs may be located in the database and will be used for tracking of products during and after the study. The logs must be updated when product is received, opened, implanted, explanted, disposed of or returned to Medtronic. The disposition log tracks product information including, but not limited to, date, model/serial number, and expiration date for received product, subject ID of implanted subject, date implanted, date explanted (if applicable), date returned to Medtronic and reason for return (if applicable), reason for and method of destruction/disposal for explanted components not returned to Medtronic (if applicable), and name of person responsible for return or destruction/disposal (if applicable). Medtronic will perform periodic reconciliation of investigational product to ensure traceability.

The following products will be tracked on a disposition log:

- Reveal LINQ™ device
- 2090 Programmer with the LINQ™ HF investigational RAMware
- Patient Assistants provided to sites for use during in-office visits
- Holter DR220

The **2090 Programmers** used in the study are commercially available, however once the LINQ™ HF investigational RAMware is downloaded onto the 2090 Programmers in this study, the 2090 Programmer becomes investigational. The 2090 Programmer disposition logs will be located in the database and will be used for tracking of all programmers downloaded with LINQ™ HF investigational RAMware. When the LINQ™ HF investigational RAMware is installed on or removed from the programmer(s), the programmer disposition log must be updated.

The **Reveal LINQ™ device** used in this study are commercially available, however once the LINQ™ HF investigational RAMware is downloaded to the device, the device will be considered an investigational product. The investigational device will be tracked via device disposition logs in the database. When the LINQ™ HF investigational RAMware is installed on or removed from the device(s), these changes must be recorded on the applicable eCRF(s) (e.g. Insertion Procedure, Scheduled Follow-up or Study Exit eCRF).

9.1 Medtronic Supplied Equipment Accountability

All explanted product should be returned to Medtronic for analysis according to local laws and regulations. If the products are explanted but not returned, a justification is

required to be reported on the appropriate eCRF(s) and/or disposition log(s). The Product Distribution Logs must be updated for explanted devices. To receive a Returned Product Mailer Kit, please contact your local Medtronic personnel or Study Manager. All unused product must be returned to Medtronic upon study closure at the center.

The Product Disposition Logs must be updated with the final device disposition.

Table 9: Final Disposition of Products

Model Number	Component	Return to MDT at Center closure	Disposal after Each Use	LINQ™ HF Investigational RAMware Removal
LNQ11	Reveal LINQ™	X (Explant Only)		X (Study Exit)
24950	MyCareLink® Monitor	Return Not Required – Market Released		
96000	Patient Assistant*	Return Not Required – Market Released*		
2090	2090 Programmer with LINQ HF Research System, Rev 1.0 RAMware (or subsequent version)	X ¹		X
DR220	Holter	X		
¹ If the 2090 programmer was supplied to the site for purposes of the study, the 2090 programmer should be returned to Medtronic. All product returns will be contingent on local laws and regulations. All Investigational Product will be labeled Investigational.				

*Patient Assistants that will be used at the sites are required to be returned to Medtronic at the end of the study.

9.1.1 Shipment of Study Components

Medtronic will only allow shipment of the study device and components to the hospital or investigator when Medtronic has received all required documentation and has notified the site of readiness. Products shall be used in these centers only and according to the CIP. Clinical investigational devices and components that are used for purposes of the study only will be provided at no cost by Medtronic. Distribution of the study device and components to centers during the study will be managed by Medtronic.

All investigational components must be stored in a secure location in which access is limited to authorized personnel only.

9.1.2 Storage and Handling of Study Device and Components

It is the responsibility of the investigator to store the study specific components and study specific equipment in a secured and temperature controlled area. The method of storage shall prevent the use of the study device and components for other applications. Opening sealed cases is forbidden for other than study use and must be reported to the Investigator and Sponsor upon detection.

10 STUDY DEVIATIONS

A study deviation is defined as an event within a study that did not occur according to the Clinical Investigation Plan or the Clinical Trial Agreement.

Prior approval by Medtronic is expected in situations where the investigator anticipates, contemplates, or makes a conscious decision to deviate. Prior approval is not required when a deviation is necessary to protect the safety, rights or well-being of a subject in an emergency or in unforeseen situations beyond the investigator's control (e.g. subject failure to attend scheduled follow-up visits, inadvertent loss of data due to computer malfunction, inability to perform required procedures due to subject illness).

For medically justifiable conditions which preempt a subject's ability to complete a study-required procedure, it may be permitted to report only one deviation which will apply to all visits going forward. This may also apply for other unforeseen situations (e.g. the subject permanently refuses to complete a study required procedure and the data will not contribute to the primary end point analysis). However, prior approval from Medtronic is required for such situations.

All study deviations must be reported on the Case Report Form regardless of whether medically justifiable, pre-approved by Medtronic, an inadvertent occurrence, or taken to protect the subject in an emergency. Multiple deviations of the same type at the same visit may be reported on one case report form. In the occurrence of a corrupted device interrogation file, Medtronic may request a deviation to document that a readable interrogation file is unavailable.

In the event the deviation involves a failure to obtain a subject's consent, or is made to protect the life or physical well-being of a subject in an emergency, the deviation must be reported to the IRB as well as Medtronic within five (5) working days. Reporting of all other study deviations should comply with IRB policies and/or local laws and must be reported to Medtronic as soon as possible upon the center becoming aware of the deviation. Reporting of deviations must comply with IRB policies, local laws, and/or regulatory agency requirements. Refer to Investigator Reports, Table 15 for deviation reporting requirements and timeframes for reporting to Medtronic and/or regulatory bodies.

Medtronic is responsible for analyzing deviations, assessing their significance, and identifying any additional corrective and/or preventive actions (e.g. amend the Clinical Investigation Plan, conduct additional training, terminate the investigation). Repetitive or serious investigator compliance issues may result in initiation of a corrective action plan with the investigator and site, and in some cases, necessitate suspending enrollment until the problem is resolved or ultimately terminating the investigator's participation in the study. Medtronic will provide center-specific reports to investigators summarizing information on deviations that occurred at the investigational site on a periodic basis.

11 ADVERSE EVENTS AND DEVICE DEFICIENCIES

Timely, accurate, and complete reporting and analysis of safety information for clinical studies are crucial for the protection of subjects. Reporting and analysis of safety data are mandated by regulatory authorities worldwide. Medtronic has established procedures in conformity with regulatory requirements to ensure appropriate reporting of safety information. This study is conducted in accordance with these procedures and regulations.

11.1 Adverse Event and Device Deficiency Definitions

Where the definition indicates “device”, it refers to any device used in the study. This might be the device under investigation, or any market released component of the system.

Table 10: Adverse Event Definitions

General	
Adverse Event (AE) (Adapted from ISO 14155:2011, 3.2)	Any untoward medical occurrence, unintended disease or injury, or untoward clinical signs (including abnormal laboratory findings) in subjects, users or other persons, whether or not related to the investigational medical device NOTE 1: This definition includes events related to the investigational medical device or the comparator. NOTE 2: This definition includes events related to the procedures involved.
Adverse Device Effect (ADE) (ISO 14155:2011, 3.1)	Adverse event related to the use of an investigational medical device NOTE 1: This definition includes adverse events resulting from insufficient or inadequate instructions for use, deployment, implantation, installation, or operation, or any malfunction of the investigational medical device. NOTE 2: This definition includes any event resulting from an error use or from intentional misuse of the investigational medical device.
Device Deficiency (DD) (ISO 14155:2011, 3.15)	Inadequacy of a medical device with respect to its identity, quality, durability, reliability, safety or performance. NOTE 1: Device deficiencies include malfunctions, use errors and inadequate labeling
Relatedness	
Procedure Relatedness	An adverse event that occurs due to any procedure related to the insertion or surgical modification of the Reveal LINQ™ device
Reveal LINQ™ System Relatedness	An adverse event that results from the presence or performance of any component of the Reveal LINQ™ system (including the LINQ™ device, incision/insertion tools, patient assistant and programmer)
Seriousness	


Serious Adverse Event (SAE) (ISO 14155:2011, 3.37)
	
Adverse event that a) led to death, b) led to serious deterioration in the health of the subject, that either resulted in 1) a life-threatening illness or injury, or 2) a permanent impairment of a body structure or a body function, or 3) in-patient or prolonged hospitalization, or 4) medical or surgical intervention to prevent life-threatening illness or injury or permanent impairment to a body structure or a body function, c) led to foetal distress, foetal death or a congenital abnormality or birth defect
 
NOTE 1: Planned hospitalization for a pre-existing condition, or a procedure required by the CIP, without serious deterioration in health, is not considered a serious adverse event.

Serious Adverse Device Effect (SADE) (ISO 14155:2011, 3.36)
	
Adverse device effect that has resulted in any of the consequences characteristic of a serious adverse event.

Complication
	
An adverse event that includes the following is considered a complication:  Results in death,  Involves any termination of significant device function, or  Requires an invasive intervention
 
(21 CFR 812) Non-invasive: when applied to a diagnostic device or procedure, means one that does not by design or intention:  Penetrate or pierce the skin or mucous membranes of the body, the ocular cavity, or the urethra, or  Enter the ear beyond the external auditory canal, the nose beyond the nares, the mouth beyond the pharynx, the anal canal beyond the rectum, or the vagina beyond the cervical os.
 
For purposes of this part, blood sampling that involves simple venipuncture is considered noninvasive, and the use of surplus samples of body fluids or tissues that are left over from samples taken for non-investigational purposes is also considered noninvasive.

Observation
	
Any adverse event that is not a complication.


Unanticipated Adverse Device Effect (UADE) (21 CFR 812.3(s))
	
Any serious adverse effect on health or safety or any life-threatening problem or death caused by, or associated with, a device, if that effect, problem, or death, was not previously identified in a nature, severity, or degree of incidence in the investigational plan or application (including a supplementary plan or application), or any other unanticipated serious problem associated with a device that relates to the rights, safety, or welfare of subjects.

Other
	

Unavoidable Adverse Event	An Adverse Event inherent to a surgical procedure that is expected to occur in all subjects for a projected duration according to the Investigator's opinion, including, but not limited to:	
	Event Description	Timeframe (hours) from the Surgical Procedure
	Pocket site / Incisional pain	72
	Mild to moderate bruising / ecchymosis	168

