7 METHODOLOGY

7.1 Study Design

The Reveal LINQ™ HF study is a prospective, non-randomized, multi-center, observational, pre-market clinical study. The study is expected to be conducted at up to 30 centers in the United States. Up to 300 subjects will be enrolled to achieve approximately 40 heart failure events (no more than two per subject contribute to the cumulative total). Study subjects will be followed for up to 3 years post-insertion or until official study closure defined as when Medtronic and/or regulatory requirements have been satisfied per the Clinical Investigation Plan and/or by a decision by Medtronic or regulatory authority, whichever occurs first. Accordingly, the expected total study duration is approximately 4 years, representing approximately 1.5 years of patient enrollment and 2.5 years of subject follow-up. All Reveal LINQ™ system and procedure-related adverse events will be collected and reported per the study protocol.

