11.2 Adverse Event and Device Deficiency Assessment

11.2.1 Adverse Events

Reveal LINQ™ system and procedure-related adverse events will be collected throughout the study duration, starting at the time of signing the Patient Informed Consent Form. Reporting of these events to Medtronic will occur on an Adverse Event (AE) Form, including a description of AE, date of onset of AE, date of awareness of site, treatment, resolution, assessment of both the seriousness and the relatedness to the investigational device. Each AE must be recorded on a separate AE Form. Subject deaths are also required to be reported on a Subject Death form. Refer to section 11.6 for Subject Death collection and reporting requirement

Documented pre-existing conditions are not considered AEs unless the nature or severity of the condition has worsened. The unavoidable Adverse Events, listed in Table 9 need not be reported unless the adverse event worsens or is present outside the stated timeframe post-implant. For AEs that require immediate reporting (refer to Table 11), initial reporting may be done by phone, fax, or on the eCRF completing as much information as possible. The AE eCRF must be completed as soon as possible.

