11.3 Adverse Events and Device Deficiency Classification

All reported adverse events and device deficiencies will be reviewed by a Medtronic representative. AEs will be classified according to the definitions provided.

Upon receipt of adverse events at Medtronic, a Medtronic representative will review the adverse event/device deficiency for completeness and accuracy and when necessary will request clarification and/or additional information from the Investigator. Medtronic will utilize MedDRA, the Medical Dictionary for Regulatory Activities, to assign a MedDRA term for each adverse event based on the information provided by the investigator.

Regulatory reporting of AEs and device deficiencies will be completed according to local regulatory requirements. Refer to Table 11 for a list of required investigator and Medtronic reporting requirements and timeframes. It is the responsibility of the investigator to abide by any additional AE reporting requirements stipulated by the IRB responsible for oversight of the study.

For emergency contact regarding a UADE and/or SAE, contact a clinical study representative immediately (refer to the study contact list provided in the center’s study documents binder/investigator site file or refer to the contact information provided in Table 1).

Adverse Events and Deaths will be classified according to the standard definitions as outlined below:

Table 11: Adverse Event Classification Responsibilities

What is classified?	Who classifies?	Classification Parameters
Relatedness	Investigator	Procedure, Reveal LINQ™ system
	Sponsor	Procedure, Reveal LINQ™ system
Seriousness	Investigator	SAE
	Sponsor	SAE, UADE
Diagnosis	Investigator	Based on presenting signs and symptoms and other supporting data
	Sponsor	MedDRA term assigned based on the data provided by Investigator
Death Classification	Investigator	Sudden Cardiac, Non-sudden Cardiac, Non-Cardiac, Unknown

An independent Clinical Events Committee (CEC) will review events and provide a final adjudication of the relatedness for all events as well as the complication/observation classification for system or procedure related events. Additionally, the CEC will provide an adjudication of the death classification for all reported deaths.

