7.10. Safety Evaluation

All adverse events that are Reveal LINQ™ system-related or procedure-related are reported with onset occurring between a subject's consent and exit will be summarized. An overall summary table will be generated that shows the number of events and number and percentage of subjects that experience adverse events for each category of seriousness, complication/observation status, whether the event is

This document is electronically controlled. Printed copies are considered uncontrolled.

Confidential

an Unanticipated Adverse Device Effect (UADE) or Unanticipated Serious Adverse Defice Effect (USADE), and each level of relatedness to the procedure and/or Reveal LINQ™ system.

Adverse events will each be assigned a Medical Dictionary for Regulatory Activities (MedDRA) term, and will be summarized by MedDRA preferred term. The statistics will include the number of adverse events assigned that term, the corresponding number and percentage of subjects who experienced such an adverse event. A second column in the table will include similar statistics for the number of serious adverse events for each corresponding MedDRA term, and the number of subjects experiencing those serious adverse events. Separate tables will be done in this way for all adverse events, for just the procedure-related adverse events, and the Reveal LINQ™ system-related adverse events.

If any adverse event is classified by the CEC as an Unanticipated Adverse Device Effect, it will be summarized.

A listing table of all adverse events will also be generated. Each row will contain the subject ID, the MedDRA preferred term, the onset date and days post-procedure, whether the event was a complication or observation, whether the event was serious, the relatedness to the procedure or system (if any), a summary of actions taken in response to the event, and the outcome of the event (whether it was resolved, and the date of resolution).

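### Harm from study procedures other than insertion or surgical modification of the device, chiefly the 6-minute hall walks and study blood draws, has no adverse-event category and is missing from the safety tables.

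*Combined protocol and SAP*

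**What the plan says.** **Collection rule.** Protocol 7.1 says that all Reveal LINQ "system and procedure-related adverse events will be collected and reported per the study protocol". Section 11.2.1 repeats this with a start date: LINQ "system and procedure-related adverse events will be collected throughout the study duration, starting at the time of signing the Patient Informed Consent Form". The required-data lists for the insertion, follow-up and exit visits (8.9, 8.10, 8.16) use the same restriction.

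**Definitions (Table 10).** Procedure relatedness is "An adverse event that occurs due to any procedure related to the insertion or surgical modification of the" LINQ device. System relatedness is "An adverse event that results from the presence or performance of any component of the Reveal LINQ™ system"; the components named are the device, the incision and insertion tools, the Patient Assistant and the programmer.

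**Classification (Table 11).** The relatedness categories open to the investigator and the sponsor are "Procedure, Reveal LINQ™ system", and nothing else.

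**Analysis.** SAP 7.10 covers AEs that are "system-related or procedure-related are reported with onset occurring between" consent and exit.

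**Study procedures.** Under protocol 8.18, "Subjects will be asked to perform a 6 Minute Hall Walk test at the 1 Month, 6 Month and 12 Month office visits". Sections 8.8 and 8.10 require laboratory results at baseline, 6 and 12 months.

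**Broader wording elsewhere.** Note 2 to the general AE definition in Table 10 reads "This definition includes events related to the procedures involved", with no limit to insertion. Section 12.1 lists, as a risk-minimisation measure, that health is assessed for adverse events at every required office visit, without restricting the cause.

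**The concern.** Collecting only related AEs is a reasonable choice for an observational study of a market-released device with added software. It is harder to justify a definition of related that leaves out procedures the study itself imposes, and the protocol gives no reason for doing so.

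The subjects have NYHA Class III heart failure and are asked to exert themselves three times for the study. Section 12.3 counts the in-office visits as a potential benefit, while one kind of harm arising at those visits has no AE record. The unredacted text of section 12 and Table 14 does not mention the walk or the blood draw as a source of risk. Appendix K dispenses with a data monitoring committee partly because the CEC is considered sufficient, and the CEC can adjudicate only what is reported to it. At stake is the completeness of the safety summary; the primary objective is not affected.

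**Working it through.** The plan states no figure on this point, so the check sets the provisions side by side and then counts the procedures affected.

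**Step 1: does a category exist?** Each example is tested against Table 10.

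| Event | Due to insertion or surgical modification? | Due to presence or performance of a system component? | AE category |
|---|---|---|---|
| Pocket infection | Yes | Possibly | Yes |
| Fall with soft-tissue injury on a hall walk | No | No | None |
| Injury from a study blood draw | No | No | None |
| Harm from the DR220 Holter on the 6-month walk | No | Unclear: listed in Tables 4 and 6, not named in Table 10 | Unclear |
| Harm from RAMware download or removal | No | Arguably yes, through the device or programmer | Arguably yes |

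The gap is clear for the walk and the blood draw, open for the Holter, and probably absent for the RAMware steps.

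**Step 2: does other text widen the rule?** Note 2 in Table 10 says what counts as an AE, and 12.1 says what is assessed at visits. Neither says that such events are to be collected. Sections 7.1, 8.10, 11.2.1 and SAP 7.10 all state the narrower scope, so the explicit definition governs.

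**Step 3: which other routes exist?**
- *Deaths.* All are reported (11.5.1) and reviewed by the CEC, but Table 13 again offers only procedure and system relatedness.
- *Cardiovascular healthcare utilizations.* These are collected (8.14), including a scheduled clinic visit at which the subject has cardiovascular symptoms. Section 7.4 and SAP 7.11 send utilizations to the CEC; 11.6 sets a narrower minimum, the heart failure events of 14.2.5.
- *Non-cardiovascular injury.* The documents give no route unless it is fatal.

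**Step 4: scale.**
- Walks: 3 per subject (8.18) x up to 300 subjects (7.1) = at most 900.
- Laboratory time points: 3 per subject (8.8, 8.10) x up to 300 = at most 900, of which 2 x 300 = 600 are at follow-up visits.

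Both are ceilings, since dropout, death and early closure reduce them. The documents give no rate of adverse events per walk. As an assumption for scale only, 0.1% to 1% per walk gives 900 x 0.001 = 0.9 to 900 x 0.01 = 9 walk-related events of any kind. The number lost would be smaller, because the routes in Step 3 catch some of them.

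**The case against.** The strongest reply is that the restriction is deliberate, is stated consistently, and suits a non-significant-risk observational study. A general AE definition adapted from a standard can sit above a narrower collection rule without contradiction. Cardiovascular harm, the main worry in this population, has other routes: utilization reports, death reports, symptom review at each office visit, and the device's own arrhythmia detection. A walk that cannot be done because of illness is a reportable deviation, and SAP 7.1.2 tabulates deviations by type.

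Much of this stands. It rules out several stronger readings that a reader might infer:
- *The CEC and sponsor would be blind to harm from walks.* Not supported: deaths and cardiovascular utilizations are collected and reviewed.
- *Holter injury is certainly excluded.* Not supported: the DR220 is in both system component tables, and Table 10's list of components is introduced as inclusive.
- *Nothing before insertion could qualify as related.* Not supported: procedures related to the insertion can include preparation for it.
- *The serious-AE note about procedures required by the protocol shows that their harms were meant to be collected.* Not supported: that note is an exclusion for planned hospitalization.
- *Utilization forms cannot record relatedness.* This cannot be judged, because the case report forms are under separate cover.

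The reply does not cover non-cardiovascular injury, an AE-level record, or attribution to the walk or blood draw. If some sites read procedure-related loosely and report such events while others follow Table 10, the counts would differ by site, which also calls for clearer wording.

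**Conclusion.** The point holds within these limits. As written, harm from the hall walks and study blood draws is neither an AE for collection nor attributable to the procedure that caused it, and SAP 7.10 would not show it. The loss is mainly non-cardiovascular injury, AE-level recording and attribution. The exposure is at most 900 walks plus the scheduled blood draws; the number of events is unknown. A reader might want to compare it with the expected number of insertion-related events, but the documents give no rate for either, so no comparison can be made.

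The conclusion rests on the Table 10 definition controlling the term procedure-related in 11.2.1, and on no unseen form or handbook widening it. It is an inexpensive improvement to patient safety reporting and does not threaten the study's objective.

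**What to change.** 1. In Table 10, extend procedure relatedness to any other procedure the protocol requires, naming the hall walk and the study blood draw.
2. State in Table 10 whether the DR220 Holter is a system component.
3. In Table 11 and on the AE form, add a relatedness option for other study procedures, distinct from insertion or modification. Keep Table 13 consistent.
4. In SAP 7.10, report that option on its own row, so that insertion-related counts are unchanged.
5. Align 7.1, 11.2.1 and 12.1 with the revised scope.

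The cost is wording changes, one form option, and a few more AE forms and CEC reviews. Table 10's unavoidable-event list covers surgical procedures, so the sponsor should also say whether minor bruising after a blood draw is reportable. No visit, test, sample size or endpoint changes.
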